### 3.2.3.2. Survival Follow-up

After completing the Safety Follow-up Visit(s), subjects will be followed and contacted every 3 months until death, lost to follow-up, withdrawal of consent to further follow-up, or study closure to collect information related to:

- Survival,
- Subsequent MDS/AML-related therapies,
- Disease transformation to AML (for MDS subjects only).

This follow-up will continue until the last active subject completes at least 12 months of treatment and/or follow-up unless additional follow-up is needed to evaluate time-to-event endpoints (eg, progression-free survival [PFS] and survival). Follow-up contacts will be conducted every 3 months by telephone unless special circumstances exist (eg, the subject will visit the center for a nonstudy-related reason).

Females of childbearing potential should avoid becoming pregnant for 90 days after the last dose of IP and male subjects should avoid fathering a child for 90 days after the last dose of IP.

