**Table 3: Table of Events (Continued)**

Procedure/Assessment	Screening	Treatment Phase a					Follow-up Phase b		
	≤ 35 Days Prior to C1D1	Cycles 1 – 2		Cycles 3 – 6		Cycles 7+	Treatment D/C d	Safety Follow-up Visit(s) w	Additional Follow-up Contacts
		Day 1 c	Days 8, 15, 22	Day 1	Day 15	Day 1			
Hematology l	×	×	×	×	×	Day 1 and Day 15	×	×	--
Coagulation Parameters m	×	--	--	--	--	--	--	--	--
Serum Chemistry including amylase/lipase n	×	×	×	×	×	Day 1 and Day 15	×	×	--
Thyroid Function n	×	×	--	×	--	×	×	×	--
Pregnancy Testing (FCBP only) o	×	×	--	×	--	×	×	×	--
Safety Assessments									
Assessing Adverse Events including AESIs	After signing ICF, until 28 days after the last dose of subcutaneous azacitidine (90 days after the last dose of durvalumab) or the Treatment Discontinuation Visit, whichever date is later								--
Monitoring for Transformation to AML (only for MDS subjects)	After signing ICF and until death, lost to follow-up, withdrawal of consent for further data collection, or end of trial								
Concomitant Medications, Therapies, and Procedures	From ICF signature until 28 days after the last dose of subcutaneous azacitidine (90 days after the last dose of durvalumab) or the Treatment Discontinuation Visit, whichever date is later								--
Disease Assessments									
Bone Marrow Aspirate and/or Biopsy p	×	--	--	End of every 3rd cycle Day 22 p		×	×	--	--
Peripheral Blood Smear p	×	--	--	End of every 3rd cycle Day 22 p		×	×	--	--
Cytogenetic Testing p	×	--	--	End of every 3rd cycle Day 22 p		×	×	--	--
CCI [REDACTED] Pharmacokinetic Assessments									
CCI [REDACTED]									
Bone marrow aspirate and/or biopsy sampling for cytogenetics, % plasma cells, CCI [REDACTED]	×	--	--	End of every 3rd cycle Day 22 p		×	×	--	--

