### 6.15. Follow-up

All subjects discontinued from treatment with IP for any reason will be followed for a period of at least 28 days after the last dose of subcutaneous azacitidine and 90 days after the last dose of durvalumab or until the date of the treatment discontinuation visit, whichever is later. During Safety Follow-up Visits, the following assessments will be performed:

- AEs including AESIs (monitored until 28 days after last dose of subcutaneous azacitidine or 90 days after last dose of durvalumab)
- physical examination
- vital signs
- body weight
- ECOG performance status
- hematology
- serum chemistry (to include amylase and lipase)
- thyroid function tests
- pregnancy testing (FCBP only)

- urinalysis
- concomitant medications, therapies and procedures
- transfusion assessment
- subsequent MDS/AML therapies
- survival

Females of childbearing potential should avoid becoming pregnant for at least 90 days after the last dose of IP and male subjects should avoid fathering a child for at least 90 days after the last dose of IP. The ICF will address any country-specific requirements, as needed.

All subjects discontinued from protocol-prescribed therapy for any reason will also be contacted by telephone every 3 months (12 weeks  $\pm$  14 days) following the Safety Follow-up Visit(s) until the last active subject reaches 12 months of treatment, unless additional follow-up is needed to evaluate time-to-event endpoints (eg, PFS and survival), or until death, lost to follow-up, withdrawal of consent to further follow-up, or study closure to collect information related to:

- survival
- subsequent MDS/AML therapies
- disease transformation to AML (only for MDS cohort subjects).

The Investigator must make every effort to obtain information regarding the subject's follow-up status. All attempts to contact the subject must be documented and appropriate due diligence must be demonstrated before the subject can be considered lost to follow-up (eg, 3 unsuccessful attempts by telephone and one unanswered written attempt sent by certified or traceable post).

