#### MDS Cohort:

Progression-free survival is calculated as the time from randomization to the first documented progression or death due to any cause during or after the treatment period, whichever occurs first. Subjects who are still alive and progression free will be censored at the date of their last response assessment. The PFS curve will be estimated using KM method.

For the MDS cohort, transformation to AML and time to transformation to AML will be summarized. Time to transformation to AML is defined as the time from the date of randomization until the date the subject has documented transformation to AML. Subjects who do not transform to AML will be censored at the date of last follow-up, the date of death, or the date of study termination. Time to transformation to AML will be estimated using KM method.

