The End of Trial is defined as either the date of the last subject last visit for the completion of post-treatment follow-up, or the date of receipt of the last data point from the last subject that is required for primary, secondary and/or exploratory analyses, whichever is the later date. See Section 3.3 of the protocol.

Study Treatments

Subjects will be randomized 1:1 to receive either:

Treatment Arm A: Subcutaneous azacitidine (75 mg/m² daily for 7 days every 4 weeks [Q4W]) in combination with intravenous (IV) durvalumab at a dose of 1500 mg on Day 1 Q4W,

Or

Treatment Arm B: Subcutaneous azacitidine alone at the dose of 75 mg/m² daily for 7 days Q4W.

Table 2: Study Endpoints

Endpoint	Name	Description
MDS Cohort		
Primary	Overall response rate	Proportion of MDS subjects achieving an overall response (CR, mCR, PR or HI), based on IWG 2006 response criteria (Appendix 17.2).
Secondary	Time to response	Time from randomization to first documented response according to IWG 2006 response criteria (Appendix 17.2).
	Relapse-free survival	Time from the date CR or PR is first documented until the date of documented relapse, death from any cause, or lost to follow-up, whichever occurs first according to IWG 2006 response criteria (Appendix 17.2).
	Cytogenetic response (CyCR)	Proportion of subjects achieving complete cytogenetic response or partial cytogenetic response according to IWG 2006 response criteria (Appendix 17.2).
	Progression-free survival (PFS)	Time from randomization to the first documented PD, relapse or death due to any cause, whichever occurs first.
	Duration of response	Duration of response is defined as the time from first response observed (CR, mCR, PR or HI) until relapse, PD or death as defined by the IWG 2006 criteria (Appendix 17.2).
	Time to AML transformation	Time from randomization to AML transformation defined by at least 30% of myeloblasts either in the bone marrow or the peripheral blood.
	Transformation to AML	Proportion of subjects with disease transformation to AML.
AML Cohort		
Primary	Overall response rate	Proportion of AML subjects achieving an overall response (CR or CRi) based on modified IWG 2003 response criteria for AML. (Appendix 17.3).
Secondary	Time to response	Time from randomization to first documented response based on modified IWG 2003 response criteria for AML (Appendix 17.3).

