Progression-free survival is calculated as the time from randomization to the first documented progression, relapse or death due to any cause during or after the treatment period, whichever occurs first. Subjects who are still alive and progression-free will be censored at the date of their last response assessment. The PFS curve will be estimated using KM method.

Median PFS along with two-sided 95% CI will be provided for each cohort and treatment group. The PFS at 6 and 12 months will be estimated and compared using Kaplan-Meier (KM) method.

A sensitivity analysis of PFS will be performed, censoring PFS at the time of subsequent systemic anticancer therapy if the subject did not progress before that time.

Transformation to AML and Time to AML Transformation

Number of subjects with transformation to AML and time to transformation to AML will be summarized. Time to transformation to AML is defined as the time from the date of randomization until the date the subject has documented transformation to AML (at least 30% of BM blats). Subjects who do not transform to AML will be censored at the date last disease assessment date. Median time to transformation to AML and associated two-sided 95% CI will be estimated using KM method.

AML Cohort:

HI

Rate of HI – erythroid response (HI-E), hematological improvement – platelet response (HI-P) and hematological improvement – neutrophil response (HI-N) according to IWG 2006 response criteria for MDS ([Appendix 17.2](#)), will be provided together with Wald asymptotic two-sided 95% CIs.

Table 4: Event and Censoring Rules for Progression-free Survival, Duration of Response, Time-to-Response and Relapse-free Survival

Situation	Date of Progression or Censoring	Situation Outcome
Censoring Rules for PFS and DoR		
Progression	If the first PD is a scheduled assessment then Date of first PD; If the first PD is an unscheduled assessment and no previous assessment, then Date of PD; If the first PD is an unscheduled assessment and has previous assessment, then Date of previous assessment (regardless of the response type).	Event
Death between scheduled assessments or within the first two missed scheduled assessments	Date of death	Event
No progression	Date of last adequate assessment with evidence of no PD	Censored
Death or progression after two or more missed scheduled assessments	Date of last adequate assessment with evidence of no PD; if no adequate assessment exists then censored at date of first dose	Censored

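### Time to AML transformation: the SAP sets no on-treatment limit on events but censors subjects without transformation at the last disease assessment, so event-free follow-up after treatment is lost

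*SAP*

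**What the plan says.** **Event.** SAP 10.2 measures from randomization "until the date the subject has documented transformation to AML (at least 30% of BM blats". SAP Table 2 is slightly wider: "Time from randomization to AML transformation defined by at least 30% of myeloblasts either in the bone marrow or the peripheral blood". Neither limits the event to the treatment period.

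**Censoring in the SAP.** "Subjects who do not transform to AML will be censored at the date last disease assessment date".

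**Censoring in the protocol.** Protocol 9.6.1.2 says that subjects who do not transform "will be censored at the date of last follow-up, the date of death, or the date of study termination".

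**When disease is assessed.** The Disease Assessments block of protocol Table 3 lists marrow, blood smear and cytogenetics. They are scheduled at the end of every third cycle and at treatment discontinuation. Both follow-up columns are blank.

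**When transformation is collected.** Table 3 sets the monitoring window: "After signing ICF and until death, lost to follow-up, withdrawal of consent for further data collection, or end of trial". Protocol 3.2.3.2 and 6.15 include transformation among the items asked at the 3-monthly telephone contacts. Protocol 6.6.2 and 10.7.1 make it reportable as a serious event throughout the study, and 6.6.2 asks for supporting histology or cytology.

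**Declared changes.** SAP section 15 lists changes to response derivations, the interim analysis and the efficacy evaluable population. It does not mention this censoring rule.

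**The concern.** The event and the censoring date run on different clocks. As an example, suppose two subjects both stop treatment at month 5 and have their last marrow then. One has a documented transformation at month 11 and is an event at month 11. The other is reached at month 17, still free of transformation, and is censored at month 5. The first is in the risk set at month 11 and the second is not, only because of what happened later. Censoring therefore depends on the outcome, which Kaplan-Meier and log-rank methods do not allow.

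The curve would then overstate transformation, and more so the shorter the treatment. SAP 10.2 says that time-to-event data are compared between arms by a stratified log-rank test. If the arms differed in treatment duration, a difference could appear with equal true hazards.

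Elsewhere the SAP guards against this. Table 4 censors progression or death after two or more missed assessments for PFS and duration of response, with a matching row for RFS. Overall survival censors subjects lost to follow-up at last contact. Time to transformation has neither provision.

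**Working it through.** The documents state no expected rate, event count or power for this endpoint, so there is no planned figure to reproduce. The check has two parts.

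**1. Text.** Events can arise up to death or end of trial (Table 3, 3.2.3.2, 6.6.2, 6.15, 10.7.1). Under the SAP, event-free time ends at the last disease assessment, which Table 3 schedules no later than discontinuation. The protocol rule ends it at last follow-up, death or study termination, which matches the collection window.

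**2. Size, by simulation.**

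Inputs:
- Follow-up uniform over 12 to 27 months: 15 months of enrollment plus 12 months after the last subject (protocol 3.1).
- Marrow every 84 days on treatment (every third 28-day cycle) and at discontinuation.
- Assumed: transformation time T exponential with 25% at 12 months, so the hazard is -ln(0.75)/12 = 0.0240 per month; death exponential with median 24 months; treatment duration D exponential with median 10 or 6 months; all independent.
- Assumed: a share q of off-treatment transformations is documented and counted.

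With C = min(death, administrative end), an event is a counted T ≤ C. Otherwise the protocol rule censors at C. The SAP rule censors at D if D < C, and at the last scheduled marrow before C if treatment is ongoing.

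Kaplan-Meier estimate at 12 months (truth 25%, 400,000 subjects):

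| q | SAP rule, median treatment 10 / 6 months | Protocol rule, 10 / 6 months |
|---|---|---|
| 100% | 34% / 40% | 25% / 25% |
| 50% | 31% / 35% | 21% / 19% |
| 25% | 28% / 31% | 19% / 17% |
| 0% | 26% / 26% | 17% / 14% |

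Fewer than one subject in an arm of 36 (72/2) remains at risk at 24 months under the SAP rule, so estimates at that time should not be used.

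**Second set of rates.** The IPSS-R table in protocol Appendix H gives 25% AML evolution at 1.4 (High) and 0.7 (Very High), read here as years. The hazards are -ln(0.75)/16.8 = 0.0171 and -ln(0.75)/8.4 = 0.0342 per month, so true 12-month rates are 18.6% and 33.7%. With median survival 24.46 months (protocol 1.3.2), full documentation and median treatment from 9 down to 4 months:
- The SAP rule gives 27.5-39.5% (High) and 45.0-55.9% (Very High).
- The median time to transformation falls from 40.5 to 14.0-18.9 months (High) and from 20.2 to 10.9-13.3 months (Very High).
- Limiting events as well as censoring to the assessment period gives 19.4-19.5% and 34.9-35.2%, close to the truth.

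**Log-rank type I error.** Equal true hazards, 36 per arm, unstratified, full documentation, SAP rule:
- similar treatment durations: about 5%
- medians 6 v 10 months: about 8-9%
- medians 4 v 9 months: about 14%

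For 6 v 10 months it falls to about 6-7% with half documentation and about 5% with a quarter.

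**The case against.** The strongest reply is that the SAP never says off-treatment events count. SAP 10.2 asks for at least 30% marrow blasts, and a telephone contact yields no blast percentage. Protocol 6.7.1 names central review of marrow and blood samples as a source for monitoring transformation, and scheduled marrow sampling ends at discontinuation. The PFS definition in SAP 10.2 expressly covers the time after treatment; the transformation definition does not. If only events from assessed samples entered, censoring at the last assessment would be consistent and nearly unbiased (26% against 25%).

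This stands in part. Counting off-treatment events is an inference from an unrestricted definition combined with collection at any time. It is a fair inference, because SAP Table 2 also accepts blood blasts and protocol 6.6.2 takes in late cases with histology or cytology. The term disease assessment is also undefined for this endpoint. Hematology with percent blasts continues at the 28-day and 90-day visits (protocol 6.6.6.1), which would shorten the gap for some subjects if it qualified.

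A second objection also stands: the protocol rule is accurate only if follow-up contacts capture transformations. With a quarter or fewer documented, its downward error is at least as large as the SAP rule's upward error.

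Third, a reader might infer that the arm comparison is biased, or that one arm is favored. The documents do not support that. They state no difference in treatment duration between arms, and with similar durations type I error stays near 5%. Nor does SAP 10.2 plan a 12-month estimate here; it plans a count, a median and its confidence interval. The 12-month figures only gauge the bias.

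**Conclusion.** The censoring rule is wrong as written and departs from the protocol without being declared. To the extent that off-treatment transformations are documented and counted, the transformation curve is biased upward and the median downward. At 12 months, against a true 25%, the estimate is about 34-40% with full documentation, 31-35% with half and 28-31% with a quarter. With none it is 26%, which is nearly unbiased. These sizes rest on assumed exponential and independent times and on treatment medians of 6 to 10 months, not on trial data. Independence is a simplification, since progression is itself a reason to stop treatment.

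A false difference between arms needs clearly unequal treatment durations and good documentation: about 8-9% type I error at 6 v 10 months and about 14% at 4 v 9.

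The consequence is limited. This is one secondary endpoint in a 72-subject cohort. The primary response rate does not depend on it, and neither does the companion endpoint, the proportion transforming. It should be corrected because the planned median would be hard to interpret and the correction is cheap.

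**What to change.** In SAP 10.2:

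1. State that documented transformations at any time from randomization count, and reconcile the marrow-only wording there with the marrow-or-blood wording in SAP Table 2.
2. Censor subjects without transformation at the last date their status was known to be negative. That is the latest of marrow, hematology, safety visit, or follow-up contact with status recorded, bounded by death and data cut-off. This is consistent with protocol 9.6.1.2.
3. Add a sensitivity analysis that limits both events and censoring to the disease-assessment period. If transformations are under-reported by telephone, the rule in step 2 underestimates the rate, and this analysis shows how much the result depends on it.
4. If the sponsor prefers to keep censoring at the last disease assessment, restrict events to the same period and list the change in SAP section 15.

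The cost is a few sentences in the SAP, one changed derivation and one extra analysis. The protocol already requires the contacts and the transformation item, so no new data collection is needed.

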4.3.1. MDS Cohort

Sekeres et al ([Sekeres, 2014](#)) demonstrated that treating subjects with higher-risk MDS resulted in an overall response rate (ORR) (complete remission [CR], marrow complete remission [mCR], partial remission [PR], hematological improvement [HI]) of 36% after four cycles of azacitidine alone. This number is consistent with the “HI and better” rate from the AZA-MDS-001 trial of 36.4%.

Assuming a treatment effect of 100% relative improvement of ORR (from 36% to 72% ORR), a sample size of 72 subjects will provide a power of 90% to detect such an effect at the 5% level of statistical significance.

An interim analysis for futility purpose will be conducted on the first 30 subjects who have completed 6 cycles of treatment unless they have established an earlier response (CR, mCR, PR or HI) or discontinued due to death or disease progression. Subjects assigned to Arm A, who received less than 3 cycles of durvalumab and continued under azacitidine monotherapy are to be excluded from the interim analysis.

The MDS cohort will continue to enroll a total of 72 MDS subjects if one of the below conditions is met at the interim analysis:

- If the ORR (considering the composite score of CR + PR + mCR + HI) in the combination arm is numerically higher than or equal to the control group (azacitidine alone) or,
- If the response rate of one of the components of this composite score (in particular CR rate) in the combination arm is numerically higher than or equal to the control group (azacitidine alone) or,
- If evidence of a clinically meaningful difference in favor of the combination arm in a secondary endpoint (eg, duration of response) is provided.

If none of these conditions is met, then the cohort might be terminated. The data monitoring committee (DMC) will review the data at the time of interim analysis and will provide recommendation/advice to Celgene.

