4.3.2. AML Cohort

Studies conducted by Dombret et al and Fenaux et al ([Dombret, 2015](#); [Fenaux, 2010](#)) showed a response (CR + complete remission with incomplete blood recovery [CRi]) rate of 25% in AML subjects treated with azacitidine. Assuming a treatment effect of 100% relative improvement of CR and CRi (from 25% to 50% absolute CR and CRi rates), a sample size of 110 subjects will provide a power of 80% to detect such an effect at the 5% level of statistical significance.

An interim analysis for futility purpose will be conducted on the first 50 subjects who have completed 6 cycles of treatment unless they have established an earlier response (CR or CRi) or discontinued due to death or disease progression. Subjects assigned to Arm A, who received less than 3 cycles of durvalumab and continued under azacitidine monotherapy are to be excluded from the interim analysis.

The AML cohort will continue to enroll a total of 110 AML subjects if one of the below conditions is met at the interim analysis:

- If the ORR (considering the composite score of CR + CRi) in the combination arm is numerically higher than or equal to the control group (azacitidine alone) or,
- If the response rate of one of the components of this composite score (in particular CR rate) in the combination arm is numerically higher than or equal to the control group (azacitidine alone) or,
- If evidence of a clinical meaningful difference in favor of the combination arm in a secondary endpoint (eg, duration of response) is provided.

Durvalumab (MEDI4736)

Statistical Analysis Plan: Protocol MEDI4736-MDS-001 _____ Celgene Corporation

If none of these conditions are met, then the cohort might be terminated. The DMC will review the data at the time of interim analysis and will provide recommendation/advice to Celgene.

CELGENE PROPRIETARY INFORMATION

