10. EFFICACY ANALYSIS

All efficacy analyses will be carried out on the ITT Population. Supportive efficacy analyses will also be performed using EE Population.

All efficacy endpoints will be summarized by disease cohort and treatment arm.

All confidence intervals (CIs) will be provided at a level of 95% and between-group comparisons will be provided as appropriate as described below.

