10.1. Primary Efficacy Endpoint

The primary efficacy endpoint is the ORR and will be programmatically derived using the results/assessments generated by the central morphologic/cytogenetic and hematology laboratories. In case no central hematology results are available within +/- 8 days of bone marrow samples, local hematology results might be used if available. This analysis will be conducted after completion of the Stage 1 and Stage 2 portions of the study. A subject is considered evaluable for response if they have undergone at least one disease status assessment following treatment Cycle 6. Subjects who discontinue from the treatment phase before the first post baseline efficacy assessment (following treatment Cycle 3) will be replaced unless the subject had a documented progression of their disease or died and will be considered as non-responders. If one post baseline disease assessment is performed, this assessment would be considered for response.

The difference of the proportions for overall response between the azacitidine alone and combination therapy arms will be tested using a standard Wald asymptotic two-sided test with unpooled estimate of variance and presented along with corresponding two-sided 95% CIs.

The hypothesis tested will be:

$$H_0: d = 0$$

versus

$$H_a: d \neq 0,$$

Where $d = p_1 - p_2$ is difference in overall response rate in the combination therapy arm (p_1) versus the overall response rate in the monotherapy arm (p_2).

The test statistic is

$$z = \hat{d}/se(\hat{d})$$

Where, the standard error is computed from the sample proportions as

$$se(\hat{d}) = \sqrt{\frac{\hat{p}_1(1 - \hat{p}_1)}{n_1} + \frac{\hat{p}_2(1 - \hat{p}_2)}{n_2}}$$

Where \hat{p}_1 (respectively \hat{p}_2) is the estimated response rate in the combination therapy arm (respectively monotherapy arm) and is derived as the observed response rates in respective arms.

Myelodysplastic Syndromes Cohort

For the MDS cohort, the primary efficacy endpoint is the proportion of subjects achieving an overall response rate (defined as CR, PR, mCR, and/or HI) as determined using the International Working Group (IWG) 2006 response criteria for MDS ([Appendix 17.2](#)). The ORR will be summarized together with two-sided 95% CI. Subjects discontinued before 6-cycle treatment without achieving overall response will be counted as nonresponders.

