10.2. Secondary Efficacy Endpoints

Overall response rate and best overall response will also be provided according to the investigator assessment. Of note a response reported as Cytogenetic Complete Remission (CRc) in the eCRF would also be considered as CR in the summaries, CRc being a subset of CR.

Time to event data will be compared between treatment arms within each cohort using a log-rank test stratified according to their cytogenetic risk at time of randomization (intermediate vs poor and very poor for MDS and intermediate vs poor for AML).

Response rates will be compared between treatment groups using the same methodology for the primary endpoint.

Overall Survival

Overall survival is defined as the time between randomization and death/censored date. Subjects who die, regardless of the cause of death, will be considered to have had an event. Subjects who are alive at the time of clinical data cut-off date will be censored at the earlier between last assessment at which the subject was known to be alive and cut-off date will be used. All subjects who were lost to follow-up prior to the clinical data cut-off date will also be censored at the time of last contact. The stratified log rank test will be used to compare the time-to-event curves between Arm A and Arm B. The OS curve and OS at 6 and 12 months will be estimated and compared using Kaplan-Meier (KM) method.

Time-to-Response (TTR)

Time to onset of first response is defined as the time between the date of randomization and the earliest date any response (CR, PR, mCR, or HI for MDS Cohort, CR or CRi for AML Cohort whichever is the 1st) is observed. Subjects who do not achieve any defined response during the treatment period will be censored at the date of last adequate response assessment, disease progression, or death, whichever occurs first. Median time to onset of first response and associated two-sided 95% CI for the treatment group will be estimated using the KM method.

A sensitivity analysis of TTR will be performed for subjects who had responded. Summaries using descriptive statistics n, Mean, Standard Deviation (STD), Q1 and Q3, Median, Minimum (Min), and Maximum (Max) will be provided.

Duration of Response (DoR)

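### The SAP's Wald 95% intervals for the AML hematologic improvement rates under-cover if those rates are low and collapse to 0–0 with no responders; a Wilson or Clopper-Pearson interval removes the problem

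*SAP*

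**What the plan says.** The hematologic improvement rate is a named secondary endpoint of the AML cohort (SAP Table 2; protocol Table 2). The HI paragraph at the end of SAP 10.2 states that the three component rates "will be provided together with Wald asymptotic two-sided 95% CIs". SAP 10 sets the general level, "All confidence intervals (CIs) will be provided at a level of 95" per cent, and runs the efficacy analyses on all randomized subjects.

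For comparisons between arms, SAP 10.2 states: "Response rates will be compared between treatment groups using the same methodology for the primary endpoint". SAP 10.1 defines that method as a "standard Wald asymptotic two-sided test with unpooled estimate of variance", with the standard error computed from the two observed proportions.

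Elsewhere no single-rate method is named. For the response components (SAP 10.1) and for cytogenetic response (SAP 10.2), the text asks for a two-sided 95% interval and stops there. Neither document provides an exact, score or small-count alternative, and neither gives an expected rate for HI, for the separate components or for cytogenetic response.

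**The concern.** The Wald interval for one proportion estimates its standard error from the observed rate. When few subjects respond, that standard error is too small, and with no responders it is zero. The interval then fails most at the low rates where its width matters most to the reader.

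An AML HI rate reported as 0% with an interval from 0% to 0% would tell the reader that there is no uncertainty, when about 55 subjects per arm cannot exclude a rate of several percent. A negative lower limit is an impossible value in a results table. These are error bars on a secondary endpoint, and a reader may use them to judge whether the combination has any activity on blood counts.

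**Working it through.** **Inputs.** AML total 110, power 80%, 5% level (SAP 4.3.2: "a sample size of 110 subjects will provide a power of 80% to detect such an effect at the 5% level of statistical significance", for an improvement "from 25% to 50% absolute CR and CRi rates"). MDS total 72, power 90%, for an improvement "from 36% to 72% ORR" (SAP 4.3.1). Allocation 1:1 (SAP 4.2). The true HI rate is not given, so it is varied.

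**The plan's own sample sizes.** With a two-sided 5% level and unpooled variance, n per arm = [p1(1−p1) + p2(1−p2)] × (1.960 + z_power)² / (p1−p2)².

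- AML: (0.1875 + 0.25) × (1.960 + 0.842)² / 0.25² = 54.9, so 55 per arm and 110 in total.
- MDS: (0.2304 + 0.2016) × (1.960 + 1.282)² / 0.36² = 35.02, so 36 per arm and 72 in total.

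Both totals are reproduced, so n = 55 per AML arm is used below.

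**Wald interval.** x/n ± 1.960 × √[(x/n)(1−x/n)/n], at n = 55:

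| Responders | Wald 95% interval |
|---|---|
| 0 | 0 to 0 |
| 1 | −1.7% to 5.4% |
| 2 | −1.3% to 8.6% |
| 3 | −0.5% to 11.5% |
| 4 | 0.4% to 14.1% |

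For 0 of 55, the Clopper-Pearson upper limit is 1 − 0.025^(1/55) = 6.5%. The Wilson upper limit is 1.960² / (55 + 1.960²) = 3.84 / 58.84 = 6.5%.

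**Coverage.** This is the sum of binomial probabilities over the counts whose interval contains the true rate. At a 2% rate the counts 1 to 5 qualify. The count 0 is lost, with probability 0.98^55 = 32.9%, and the counts of 6 or more add less than 0.1%, so coverage is 67.0%.

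| True rate | P(0 of 55) | Wald | Wilson | Clopper-Pearson |
|---|---|---|---|---|
| 1% | 57.5% | 42.4% | 89.5% | 98.2% |
| 2% | 32.9% | 67.0% | 97.6% | 97.6% |
| 3% | 18.7% | 81.1% | 97.6% | 97.6% |
| 4% | 10.6% | 89.3% | 97.8% | 97.8% |
| 5% | 6.0% | 93.5% | 94.4% | 98.1% |
| 10% | 0.3% | 91.5% | 93.4% | 95.9% |

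Wald coverage is 91.7% at a 15% rate, 92.4% at 20% and 93.4% at 25%. It does not rise smoothly with the rate. At 6%, the upper limit for 1 responder (5.35%) falls short of the true rate, so counts 0 and 1 are both lost (3.3% + 11.7%). With another 0.5% lost from counts of 9 or more, coverage is about 84%.

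**Secondary comparisons.** With no responders in either arm, z = 0/0 and the test has no result. With none in one arm, that arm contributes zero variance. Type I error by enumeration over all pairs of counts:

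| Common rate | 55 per arm | 36 per arm |
|---|---|---|
| 1% | 0.3% | 0.1% |
| 2% | 1.7% | 0.6% |
| 3% | 3.5% | 1.5% |
| 4% | 4.9% | 2.7% |
| 5% | 5.8% | 3.8% |
| 10% | 6.0% | 5.8% |

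The maximum over rates up to 50% is about 6.2% at either size, near a 7% rate with 55 per arm and near 37% with 36 per arm.

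**The case against.** The strongest reply is that low HI rates are only an assumption. The control rates used for planning are 25% (AML CR plus CRi) and 36% (MDS ORR), and at 25% the Wald interval covers about 93% with n = 55. These are secondary rates in a Phase 2 trial, no alpha is allocated to them, and the futility rules rest on numerical comparison or clinical judgement, not on these intervals. All of this stands and it limits the size of the point. It does not repair a zero-width interval or a negative limit, and the SAP has no fallback if either occurs.

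A reader might go further and infer that the test calls chance differences significant, since 0/55 v 4/55 gives z = 2.077 and p = 0.038 while Fisher's test gives p = 0.118. The documents do not support that inference. The test is conservative at common rates of 4% or less and only mildly liberal above. The result is not peculiar to the unpooled variance either: pooled z gives p = 0.042 and Barnard's exact test p = 0.045, whereas Boschloo's gives 0.085. Pairing Fisher's test with a Newcombe interval would bring a problem of its own, because for 0/55 v 5/55 Fisher gives p = 0.057 while the Newcombe interval, 0.8 to 19.6 points, excludes zero.

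A reader might also extend the coverage figures to the MDS cohort, the response components or cytogenetic response. The SAP names no Wald interval for those single rates, and cytogenetic response uses a smaller denominator of unstated size. The point there is only that the method is missing.

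**Conclusion.** The concern holds for the AML HI-E, HI-P and HI-N intervals. With about 55 subjects per arm as the denominator, the shortfall in coverage is serious if a true rate is about 3% or less. It is generally modest from 5% upward, apart from dips such as the one at 6%. Both the low rate and the use of the full arm as denominator are assumptions, since the documents give no expected HI rate. The 0-to-0 interval and the negative lower limits follow directly from the prescribed formula whenever the counts are that small.

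For the secondary comparisons, what remains is the undefined statistic at 0 v 0 and the zero variance given to an arm without responders, not a materially inflated error rate. The primary ORR conclusion is unaffected, because its planning rates lie well away from zero.

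**What to change.** In the HI paragraph of SAP 10.2, replace the Wald interval with a Wilson or Clopper-Pearson 95% interval. Name the same method for the response-component rates in SAP 10.1 and the cytogenetic response rates in SAP 10.2. Clopper-Pearson keeps coverage at or above 95% throughout. Wilson is usually narrower but drops to 89.5% at a 1% rate with n = 55. Either is a clear improvement.

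State also how the comparison will be reported when neither arm has a responder, for example as not estimable. No change of test is needed on the evidence here.

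The cost is a line or two of SAP text and a different software option. No further data or subjects are required. Intervals at low rates become somewhat wider: for 1 of 55, Wilson gives 0.3% to 9.6% in place of −1.7% to 5.4%.
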